#### **9.7.3.2 Missing AE onset date**

Adverse events with missing or incomplete onset dates will be imputed according to a BI standard algorithm, which is based on a conservative approach. In short, this approach ensures that all AEs with missing dates will be counted as “on-treatment” unless there is well-documented data showing otherwise. For the calculation of time to event, the earliest possible date on-treatment (i.e. date of start of treatment) will be used to impute missing onset dates. Partially missing onset dates will also be imputed with the corresponding earliest possible date (e.g. if only the year and month are available, use the first day of the month or the date of start of treatment, whichever is later).

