Disposition, demographics, exposure	Yes	Yes	Yes	Yes	Yes
Concomitant diagnoses and therapies	Yes	Yes	Yes	Yes	Yes
Lower limb amputation					
Frequencies	Yes	Yes	Yes	Yes	Yes
Incidence rates	Yes	Yes	Yes	Yes	Yes
Time to onset analyses	Yes	Yes	Yes	Yes	Yes
Time to onset analyses with competing risk	Yes	-	-	-	-
Sensitivity analyses (heterogeneity analyses, forest plot)	Yes	Yes	-	-	-
Adverse events related to amputations (definition based on list of PTs)					
All patients					
Frequencies	Yes	Yes	Yes	Yes	Yes
Incidence rates	Yes	Yes	Yes	Yes	Yes
Time to onset analyses	Yes	Yes	Yes	Yes	Yes
Patients with amputations only, i.e. preceding events					
Frequencies	Yes	Yes	Yes	Yes	Yes
Incidence rates	Yes	Yes	Yes	Yes	Yes
Time to onset analyses (KM only)	Yes	Yes	Yes	Yes	Yes
Lower limb amputation events occurring after the first LLA event					
Descriptive Statistics (Frequency tables with absolute and relative frequencies)	Yes	Yes	Yes	Yes	Yes
Adverse Events related to amputations occurring after the first LLA event					
Descriptive Statistics (Frequency tables with absolute and relative frequencies)	Yes	Yes	Yes	Yes	Yes

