##### *AEs related to amputation*

Subgroup analyses for SAF-M1 and SAF-M2 will be carried out.

For AEs related to amputation, analyses for different grouped events will be performed (see the SAP [[c16853237](#), Appendix 6.1]). Cumulative proportions of patients and the number of patients at risk will be provided. In addition, Cox regression analyses will be performed for vascular AEs, diabetic-foot-related AEs, wound/infection, nervous system disorders, and

volume depletion events if the sample size is statistically sufficient, i.e. at least 14 patients with events in total over the 2 treatment groups have been reported.

An ITT approach will be used as a secondary analysis, which includes all events during the observation period after starting randomised treatment, regardless if the patient was taking study medication or not when the event occurred.

A listing of AEs with onset during any treatment other than the randomised treatment will be provided.

Additionally, AEs related to amputation preceding the amputation will be summarised for patients with amputation; AEs with onset after the amputation will not be considered in the analysis of this sub-population.

AEs related to amputations occurring after the first amputation event will be summarised using descriptive statistics (frequency tables with absolute and relative frequencies).

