### **9.7.3 Handling of missing data**

#### **9.7.3.1 Missing amputation date**

In studies 1245.110 and 1245.121, the date and other details on LLA events are to be captured on eCRF pages; therefore, no missing dates are expected. However, LLA events were not specifically captured via eCRF in study 1245.25.

For any missing date of the LLA event, the date is imputed as the date of admission to the hospital or the date of the diagnosis of the event triggering the amputation, whichever is later. In case the date information is incomplete (e.g. only year and month are reported), the mid-point of the possible interval will be used according to BI standard imputation rules for concomitant therapies.

For LLA event, a sensitivity analysis will be conducted for incidence rate calculation in SAF-M1 and SAF-M2 excluding all patients with amputations with missing onset dates. This analysis will only be performed if >10% of onset dates are missing.

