4.2 ANALYSIS SETS AND HANDLING OF MISSING DATA

All analyses will be based on the treated set (TS).

For study 1245.25 the TS consists of all randomized patients who received at least one dose of study medication. Patients will be assigned to treatment groups according to their randomization.

For studies 1245.110 and 1245.121 the TS will include all patients who were dispensed study medication and were documented to have taken at least one dose of study medication. Patients will be assigned to treatment groups according to their randomization.

Missing amputation dates

In studies 1245.110 and 1245.121, the date and other details on LLA events are to be captured on eCRF pages; therefore no missing dates are expected. However, LLA events were not specifically captured via eCRF in study 1245.25. For any missing date of the LLA event, the date is imputed as the date of admission to the hospital or the date of the diagnosis of the event triggering the amputation, whichever is later.

In case the date information is incomplete (e.g. only year and month are reported), the midpoint of the possible interval is used according to BI standard imputation rules for concomitant therapies.

All missing amputation dates that were imputed will be displayed individually by study, including a narrative justification.

Missing AE onset dates (not applicable for LLA events)

For imputation of missing dates and times BI standards will be used. These are based on a conservative approach. In short, this approach ensures that all AEs with missing dates will be counted as “on-treatment” unless there is well documented data showing otherwise. For the calculation of time to event, the earliest possible date on-treatment (i.e. date of start of treatment) will be used to impute missing onset dates. Partially missing onset dates will also be imputed with the corresponding earliest possible date (e.g. if only the year and month are available, use the first day of the month or the date of start of treatment, whichever is later).

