4.3.2.2.2 Adverse events related to amputation

The types of analyses to be performed on these events are outlined in [Table 4.3:1](#). The analyses will be performed for these events based on all treated patients and in the subgroup of patients with a subsequent amputation, but for events before the actual amputation only. Events occurring after the first amputation will not be included.

Frequency tables of patients with events preceding amputations (see [Section 4.1.1.2](#)) by treatment, group of PT as specified in Appendix 6.1, SOC and PT will be provided. In addition incidence rates will be displayed.

Kaplan Meier analyses (cumulative incidence functions) for time to first event will be provided by treatment and stratified by study; hereby the analysis will not be provided on individual PT level but events being grouped into vascular AEs, diabetic foot related AEs, wound/infections or nervous system disorders and volume depletion (see [Appendix 6.1](#)). Cumulative proportion of patients and the number of patients "at risk" will be provided. In addition, Cox regression analyses will be performed for the above defined AE groups if sample size is statistically sufficient, i.e. if at least 14 patients with events in total over the 2 treatment groups have been reported.

A listing of AEs with onset during any other than randomized treatment will be provided.

AEs related to amputations occurring after the first amputation event will be analysed using descriptive statistics and will be provided in the final report.

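### Earliest-date imputation of AE onset also decides whether a related AE came before the amputation, and it can err only towards 'preceding'

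*Protocol*

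**What the plan says.** Protocol 9.7.3.2 summarises a sponsor algorithm for missing AE onset dates. An AE with a missing date is treated as on treatment "unless there is well-documented data showing otherwise". For time-to-event calculations, "the earliest possible date on-treatment (i.e. date of start of treatment) will be used to impute missing onset dates". SAP 4.2 has the same rule and adds: "Partially missing onset dates will also be imputed with the corresponding earliest possible date".

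Amputation dates follow another rule. For an incomplete LLA date, protocol 9.7.3.1 says that "the mid-point of the possible interval will be used according to BI standard imputation rules for concomitant therapies". SAP 4.2 states that the AE rule does not apply to LLA events.

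The amputee analysis is then defined by order in time. Protocol 9.7.2.1: "AEs with onset after the amputation will not be considered in the analysis of this sub-population". SAP 4.3.2.2.2: "Events occurring after the first amputation will not be included". In protocol Table 9.7: 2, the block headed "Patients with amputations only, i.e. preceding events" plans frequencies, incidence rates and KM in both pools and all three studies. A separate descriptive table covers related AEs after the first LLA.

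**The concern.** The earliest-date rule is conservative for one question: was the AE on treatment? The amputee analysis asks a different one: did the AE come before the first LLA? For an AE without a usable date, the rule supplies that answer instead of leaving it open.

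The term list makes this more than a formality. SAP Appendix 6.1 includes Post-operative wound infection, Wound dehiscence, Impaired healing and Wound necrosis, all of which can follow amputation surgery. Both documents say that outcome data continue to be collected after the first amputation, so such AEs will be in the database.

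At stake is a named exploratory objective (protocol section 8): the frequency and incidence rate of related AEs that preceded the amputation. A stump complication without a full date could be reported as a precursor of the procedure that caused it.

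**Working it through.** The plan gives no count of undated AEs, so there is no figure to reproduce. The check applies the stated rules to the possible date orders.

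**Inputs**
- Fully missing AE onset: treatment start, called day 1 (protocol 9.7.3.2, SAP 4.2).
- Partial AE onset: earliest possible day, not before treatment start (same sections).
- Partial LLA date: mid-point of the interval (protocol 9.7.3.1, SAP 4.2).
- Time at risk with an event: onset − treatment start + 1 (protocol 9.3.1, SAP 4.3).
- LLA on day L, with L ≥ 1.

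**1. Fully missing AE date.** To be classed as after the LLA, the AE would need 1 > L, which is impossible. So 100% are classed as not after. Time at risk is 1 day, or 1/365.25 = 0.0027 years.

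**2. Month known, LLA in that month.** Assume a 30-day month with uniform dates. The pairs in which the AE truly follows the LLA number 30 × 29 / 2 = 435.
- Day-1 rule: 435/435 = 100% fall on or before the LLA. In 29 pairs the LLA is itself on day 1 (a tie), so (435 − 29)/435 = 93% fall strictly before it.
- Comparator, a mid-point rule as used for partial LLA dates (day 15): pairs with L ≥ 15 number 15 × 16 / 2 = 120, and 120/435 = 28%.

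**3. Year known, LLA in that year.** Pairs: 365 × 364 / 2 = 66,430.
- Earliest-date rule: 100% on or before the LLA.
- Mid-point (day 183): 182 × 183 / 2 = 16,653, and 16,653/66,430 = 25%.

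**4. Known date parts wholly after the LLA.** A later month or year stays later after imputation: 0% misplaced. The fault is confined to fully missing dates and to partial dates whose unknown interval contains the LLA.

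**5. Direction.** For an AE that began on or after treatment start, the imputed date is never later than the true one. A true *before* therefore cannot become *after*; only the reverse can happen.

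**6. Safeguards.** The exception for well-documented data concerns on-treatment status, so it does not help with an AE that was on treatment but followed surgery. The only sensitivity analysis for missing dates concerns LLA dates, and only if more than 10% are missing. SAP 4.2 displays imputed amputation dates individually but plans nothing similar for AE dates.

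**7. Size, on assumed figures only.** Take 100 amputees. Sixty have a true preceding AE, at a mean of 1.0 year. Forty have none, with a mean of 1.5 years at risk. Of these forty, 10 to 30 have related AEs only after the LLA, and 1% to 10% of those are undated. The expected number misplaced is x = 10 × 0.01 = 0.1 to 30 × 0.10 = 3.
- Proportion: (60 + x)/100 rises from 60.0% to between 60.1% and 63.0%.
- Rate per 100 patient-years: 100(60 + x) / [60 × 1.0 + (40 − x) × 1.5 + x/365.25]. With x = 0, 6000/120 = 50.0. With x = 0.1, 6010/119.85 = 50.1. With x = 3, 6300/115.51 = 54.5.

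**The case against.** The best counter-argument is textual. The start-of-treatment sentence limits itself to time-to-event calculations, and the algorithm is given only in summary. Sorting AEs into before and after is a selection step, and neither document says that it uses imputed dates. A reader might infer that every undated AE is certain to be miscounted in every table, and the documents do not support that. The effect is direct for the KM and incidence-rate analyses of preceding events. For the frequency table and the after-LLA table it is a strong inference, because no other ordering date is offered. This limits the claim but does not remove it.

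Second, the overall figure is hard to move. The analyses count patients, so an amputee with any other dated preceding AE is already counted. SAP 4.1.2 describes related AEs as often preceding amputation. In the heart failure studies, events leading to LLA are AESIs reported under SAE rules, so their dates should be good. This stands for the overall figure. It protects single-PT rows less, because a dated precursor under another term does not help there.

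Third, a reader might make much of both dates being known only to the same month: day 1 for the AE and mid-month for the LLA. That case is nearly empty. SAP Appendix 6.2 reports one month-only date in 1245.25, and no missing LLA dates are expected in 1245.110 or 1245.121.

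Fourth, the analysis is exploratory, has no Cox model and treats both arms alike. A reader might still infer that the amputation hazard ratio is biased. It is not, because the AE rule does not apply to LLA dates. Equal treatment of the arms does not cancel the error in the preceding-AE table, however, since that table reports absolute frequencies.

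**Conclusion.** The point holds as a low-impact correction. As written, the imputation rule orders undated related AEs on or before the first LLA, and no separate rule prevents this. Preceding AEs can only be overstated and, if the same date is used, AEs after the first LLA understated.

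The size cannot be derived from the documents. The range of 60.1% to 63.0% against 60.0% rests entirely on assumed figures and shows only that the overall shift is probably small. The same-month and same-year comparisons assume uniform dates; the 100% results do not depend on that. The LLA outcome and the all-patient analyses of related AEs are unaffected by this ordering problem.

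**What to change.** In protocol 9.7.3.2 and SAP 4.2 and 4.3.2.2.2:
- State that earliest-date imputation is used for on-treatment status and for the all-patient analyses only.
- For the analyses before and after the first LLA, class an AE as preceding only if its known date parts, or the record of the event that led to the LLA, place it before the LLA.
- Show AEs whose order cannot be determined in a row of their own, labelled *order unknown*.
- Run one sensitivity analysis that counts these AEs as preceding.

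The cost is a wording change, one derived flag and slightly lower preceding-AE counts. No new data are needed.

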## **9.8 QUALITY CONTROL**

Standard operating procedures are used to guide the conduct of the studies. These procedures include internal quality audits, rules for secure and confidential data storage, methods to maintain and archive project documents, quality-control procedures for programming, standards for writing statistical analysis plans, and requirements for senior scientific review.

## **9.9 LIMITATIONS OF THE RESEARCH METHODS**

This will be a meta-analysis of 3 studies with heterogeneous patient populations. Patients with type 2 diabetes mellitus and increased cardiovascular risk (1245.25) will be pooled together with patients with chronic heart failure with preserved (1245.110) or reduced (1245.121) ejection fraction (see [Section 9.2.2](#) for more detailed eligibility criteria) in SAF-M1. In general, some heterogeneity between the studies can be expected due to the different populations involved in the trials to be pooled. The degree of heterogeneity of the treatment effect between studies will be assessed statistically and clinically/visually. For time-to-event outcomes, visual inspection of heterogeneity includes a forest plot of the individual study hazard ratios, alongside the corresponding estimate from the individual patient data meta-analysis in SAF-M1 and SAF-M2. For statistical assessment of heterogeneity, a Cox model will be provided including in addition the treatment-by-study interaction term. The p-value of

the interaction term from the Cox model in SAF-M1 and SAF-M2 will be used as a statistical measure for heterogeneity. For binary outcomes (frequencies and incidence rates of LLAs and AEs related to amputation), visual inspection of heterogeneity will be performed using forest plots. These will display the frequencies/incidence rates per treatment arm within each study, alongside the corresponding estimate from the pooled analysis in SAF-M1 and SAF-M2. For statistical assessment of heterogeneity,  $I^2$  will be calculated for the relative risk of an LLA or AEs related to amputation. If heterogeneity between studies is present, potential sources of variability will be assessed clinically and conclusions outlined in the final report.

The Cox model is based on the proportional hazards assumption. The proportional hazards assumption will be explored by plotting  $\log(-\log(\text{survival function}))$  against the  $\log$  of time by treatment group and checked for parallelism. The interaction of treatment with  $\log$  of time will be included in the model described above for an exploratory analysis. Further, Schoenfeld residuals for each covariate and treatment will be plotted against time and  $\log(\text{time})$ . If the proportional hazards assumption cannot be verified, potential sources will be assessed clinically and conclusions outlined in the final report.

Considering the potential differences in patient populations, subgroup analyses by demographic and baseline conditions will be carried out to assess any potential impact of these differences on the results (see [Section 9.3.3](#)).

For study 1245.25, LLA-related events were not pre-specified in the protocol or specifically captured on eCRF pages (see [Section 9.3.2.1](#)). Therefore, the extent of reporting may be different from studies 1245.110 and 1245.121. As details on LLA events collected in studies 1245.110 and 1245.121 (the reasons leading to LLA, the number of LLA episodes, level of LLA, etc.) are not available in 1245.25, SAF-M2 is created for the purpose of analysing these specific details.

Although approx. 14 000 patients are expected to be included in this meta-analysis (see [Section 9.5](#)), the number of studies involved is low ( $N=3$ ). The 3 studies were designed to investigate empagliflozin's effect on cardiovascular events, and not specifically designed or powered to investigate LLA events. As all 3 studies are event-driven, duration of treatment and observation will be different for each patient, which will be taken into account using "time at risk" to adjust the incidence of outcomes (see [Section 9.3.1](#)). As all 3 studies investigate patients who meet the specific study entry criteria, the patients in this meta-analysis may not exactly reflect the circumstances in which empagliflozin is used in the routine clinical practice, thereby limiting the generalisability of the results.

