## **9.5 STUDY SIZE**

This meta-analysis will be based on patients treated with at least 1 dose of study medication (“treated set”) in the 3 studies. Patients are assigned to treatment groups according to randomisation.

Study 1245.25 included 7020 patients treated with empagliflozin 10 mg (N = 2345), empagliflozin 25 mg (N = 2342), or placebo (N = 2333).

Study 1245.110 will randomise approx. 4126 patients to empagliflozin 10 mg or placebo in a 1:1 ratio. Study 1245.121 will randomise approx. 2850 patients to empagliflozin 10 mg or placebo in a 1:1 ratio. Almost all randomised patients are expected to be treated.

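### The forest plots for frequencies and incidence rates show arm rates and crude pooled arm rates without a between-arm ratio or interval, although their purpose is to show heterogeneity of the treatment effect

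*Protocol*

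**What the plan says.** Protocol 9.9 states the aim: "The degree of heterogeneity of the treatment effect between studies will be assessed statistically and clinically/visually". SAP 4.3, under Trial heterogeneity, has the same text. The plan then treats two kinds of outcome differently.

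- **Time-to-event outcomes.** The plotted quantity is an effect measure: "visual inspection of heterogeneity includes a forest plot of the individual study hazard ratios", with the pooled hazard ratio. A Cox model with a treatment-by-study interaction supplies the statistical check.
- **Frequencies and incidence rates.** The plotted quantity is a level in each arm: "These will display the frequencies/incidence rates per treatment arm within each study", next to the matching pooled estimate. The numerical companion is I², which "will be calculated for the relative risk of an LLA or AEs related to amputation". No heterogeneity measure is named for an incidence-rate ratio.

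The only pooled frequency or rate that the plan defines (Protocol 9.7; SAP 4.3, Frequency analyses and Incidence rates) is a weighted mean within each treatment group. Its study weights are that group's own patient numbers or time at risk.

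Protocol 9.9 also says that the populations are heterogeneous and that, for amputations in 1245.25, "the extent of reporting may be different from studies 1245.110 and 1245.121".

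**The concern.** The display does not match its purpose. A difference in arm rates between studies mixes baseline risk, completeness of capture and treatment effect, and the plan itself expects the first two to differ. The reader is left to judge the effect by comparing two points per study by eye, with no estimate of the contrast and no interval. The I² reported beside the plot describes a quantity that the plot does not show.

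The pooled points raise a second problem. Study 1245.25 has two active arms to one placebo arm, while the other two trials are 1:1. A within-arm weighted mean therefore gives 1245.25 more influence on the all-empagliflozin point than on the placebo point. If amputation frequency differs between studies, the two pooled points separate even when no trial shows any effect. In a safety report on amputation, that separation could be read as harm.

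**Working it through.** **Inputs.** Protocol 9.5 gives 2345 (10 mg), 2342 (25 mg) and 2333 (placebo) treated patients in 1245.25. For the heart-failure trials it says "Study 1245.110 will randomise approx. 4126 patients to empagliflozin 10 mg or placebo in a 1:1 ratio", and approx. 2850, also 1:1, for 1245.121. I assume that all randomised patients are treated and allocation is exactly equal (2063 and 1425 per arm). Amputation frequencies are not in the documents, so those below are assumptions with a range.

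**1. The plan's own total.** 2345 + 2342 + 2333 = 7020, and 7020 + 4126 + 2850 = 13 996, which agrees with the stated approx. 14 000.

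**2. Study weights in the pooled frequency.** With weight n_ji / Σ n_ji, the pooled value is Σ(events) / Σ(patients) within the arm, that is, the crude proportion.

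- Placebo: 2333 + 2063 + 1425 = 5821. Weight of 1245.25 = 2333/5821 = 40.1%.
- All empagliflozin: 4687 + 2063 + 1425 = 8175. Weight of 1245.25 = 4687/8175 = 57.3%.

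**3. Pooled points when no trial has an effect.** Let the frequency be 2% in both arms of 1245.25 and 2%/r in both arms of the heart-failure trials.

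- Placebo point = 2% × (0.4008 + 0.5992/r)
- Empagliflozin point = 2% × (0.5733 + 0.4267/r)

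| r | Placebo | All empagliflozin | Ratio |
|---|---|---|---|
| 1.5 | 1.60% | 1.72% | 1.07 |
| 2 | 1.40% | 1.57% | 1.12 |
| 3 | 1.20% | 1.43% | 1.19 |
| 4 | 1.10% | 1.36% | 1.24 |

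The 2% cancels, so the ratio depends only on r. At r = 1 it is 1.00. If the heart-failure trials had the higher frequency, it would fall below 1: at r = 0.5, (0.5733 + 0.8533)/(0.4008 + 1.1984) = 0.89.

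**4. Spread of the study points in the same scenarios.** To describe how far apart the plotted arm points lie, I computed I² of the arm frequencies across studies on the logit scale, with variance 1/[np(1−p)], inverse-variance Q and I² = max(0, (Q − 2)/Q). The plan does not calculate this. For r = 1.5, 2, 3 and 4 it is about 49%, 79%, 90% and 92% for placebo, and 62%, 84%, 91% and 93% for empagliflozin. I² of the relative risk is 0% throughout. At r = 2, with the variance of log RR equal to 1/a − 1/n_E + 1/c − 1/n_P (a and c the event counts, n_E and n_P the arm sizes), a plot of relative risks would show 1.00 (0.71 to 1.42), 1.00 (0.54 to 1.84) and 1.00 (0.48 to 2.08).

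**5. Where the weighting effect does not arise.**

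- In SAF-M2 both trials are 1:1, so 1245.110 has weight 2063/3488 = 59.1% in each arm and the pooled points are balanced.
- If the plot split the doses, the 10 mg point would give 1245.25 a weight of 2345/5833 = 40.2%, close to placebo, and the 25 mg point would come from 1245.25 alone. The plan does not say which grouping the plot uses. The figures above are for all empagliflozin, the grouping used in its Cox models.
- Incidence rates are weighted by time at risk, which is not yet known. The 2:1 allocation carries over, but the exact weights cannot be computed.

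**The case against.** The strongest reply is that effect heterogeneity is already covered in the same paragraph by the hazard-ratio forest plot, the treatment-by-study interaction and I² on the relative risk. The incidence rates use time to first event with the same censoring as the Cox analysis, so the hazard-ratio plot is a close counterpart of a rate-ratio plot. The analysis is exploratory, and finding heterogeneity leads only to clinical assessment and discussion in the report. Absolute rates by arm are also a legitimate safety display. All of this stands, and it limits the point to the display.

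Three stronger readings are tempting, and the documents do not support them.

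- A reader might infer that the plot could look homogeneous while effects differ substantially. Both arms of every study are shown, so a marked difference in one study's arms would be visible; what is missing is an estimate of the contrast and its precision.
- A reader might infer that the arm-rate plot alone could trigger a conclusion of heterogeneity, or that I² would be judged against a cut-off. Neither document states such a rule or any I² threshold. With two or three trials I² is a weak guide, but that gives no ground here for replacing it in SAF-M2.
- A reader might infer that the main treatment comparison is biased by the unequal allocation. It is not affected in this way, because the Cox model includes study as a factor.

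What the reply does not answer is that the plotted pooled arm points in SAF-M1 invite a comparison that is not adjusted for study, and that no heterogeneity measure is named for the rate ratio. Yet Protocol 9.7 and SAP 4.3 say that incidence rates may compare groups more accurately than frequencies when treatment durations differ.

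**Conclusion.** The point holds for the display. The forest plots for frequencies and incidence rates are presented as a check on heterogeneity of the treatment effect, but they show no effect estimate or interval. In SAF-M1 their pooled points can separate by a ratio of about 1.07 to 1.24 with no effect in any trial. That range assumes an amputation frequency in 1245.25 that is 1.5 to 4 times that of the heart-failure trials, planned sizes with equal allocation in the heart-failure trials, and pooling of the two doses. The direction would reverse if the heart-failure trials had the higher frequency. The hazard-ratio results, the interaction test and I² on the relative risk are unaffected. This is a worthwhile correction at almost no cost; it does not invalidate the planned heterogeneity assessment.

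**What to change.** In Protocol 9.9 and SAP 4.3 (Trial heterogeneity), specify that the forest plots for frequencies and incidence rates show, for each study, the empagliflozin/placebo relative risk and incidence-rate ratio with 95% CI. The pooled line should be a study-stratified ratio (for example Mantel-Haenszel) instead of a comparison of crude pooled arm values. Keep the arm frequencies and rates as a text column beside each line. Name a heterogeneity measure for the incidence-rate ratio to stand beside the planned I² on the relative risk, and state whether the empagliflozin column pools the two doses. The cost is a few sentences of text and one revised plot program; no new data are needed and no planned analysis is lost.
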